#### **4.2.3.2 Secondary Outcome Measures (Aim 2)**

Partner Sexual Function. Partners will complete either the IIEF (if male) or the FSFI (if female). Like the FSFI, the IIEF is a premier comprehensive sexual function measure with significant research in cancer populations, assessing multiple domains of function including desire, arousal, and satisfaction. Total scores will be used. Patient Sexual Distress. Patients will complete the 13-item validated Female Sexual Distress Scale-Revised (FSDS-R). The FSDS-R assesses the degree of distress and dissatisfaction related to a woman's sex life over the past 30 days, and has been used successfully in both observational and intervention studies with breast cancer survivors. Relationship Intimacy. The Miller Social Intimacy Scale (MSIS) is a 17-item scale assessing emotional intimacy, closeness and trust toward an individual's partner used in prior couple-based studies by our team, which was sensitive to increases in our pilot IE studies. Relationship Quality. The 7-item Dyadic Adjustment Scale (DAS-7) is an abbreviated form of the DAS that focuses on consensus in the relationship and correlates well with the full DAS. The DAS-7 distinguishes between distressed and non-distressed couples, is sensitive to change in response to couples' interventions, and shows excellent construct validity in breast cancer. Psychological distress will be assessed through depressive symptom and anxiety scales (PHQ-9 and GAD-7, respectively), which are validated and widely used in cancer and medical populations.

#### **4.2.3.3 Mediators (Aim 3)**

Patient and Partner Sexual Communication. Sexual communication is assessed through a brief 6-item version of the Dyadic Sexual Communication Scale (DSCS). The DSCS assesses the quality of communication in a couple's intimate relationship specifically related to sex that has been used successfully in cancer studies. The original scale has 13 items. However, with the aim of reducing participant burden we conducted several analyses including item response curves and correlational analyses to determine whether a shorter version of the DSCS would be valid without losing information. These analyses suggested items 2, 3, 4, 10, 11, and 12 provided 95% correlation with the larger scale. Thus we will use these items in place of the larger scale. Patient and Partner Self-Efficacy for Coping with Sexual Concerns. Self-efficacy for coping with sexual concerns is assessed through three items measuring participants' confidence in their ability to deal effectively with sexual concerns, communicate effectively about sexual concerns, and enjoy sexual intimacy despite physical limitations. These items were developed using standard methods for constructing self-efficacy scales according to social cognitive theory for the IE colorectal cancer study and have high internal consistency as a single scale (Cronbach's alpha=.91). Items use a 0-10 rating scale and reference the past week.

#### **4.2.3.4 Moderators (Exploratory Aim), Covariates and Other Measures.**

The moderators of patient age and race/ethnicity will be assessed using medical records and pre-treatment self-report survey, respectively. Covariates. Other socio-demographic characteristics (i.e., education, sexual orientation, marital and work status, income, relationship length) will be assessed through self-report. Medical comorbidity for patients and partners will be obtained by a validated self-report comorbidity measure (Self-Administered Comorbidity Questionnaire, SCQ). In order to reduce participant burden and prevent distress, we have modified this measure for patient participants by removing the item asking whether the participant has cancer. We will keep this item for partner participants. Clinical patient characteristics (e.g. menopausal status, comorbidity, types of treatments) will be obtained through medical chart review. Other Measures. We will collect data on frequency of patient sexual activities and use of sexual aids assessed with items from the PROMIS Sexual Function

measure. We also include two items that we developed and assessed in a prior prospective study in colorectal cancer that assess the extent to which sexuality is important to the individual, based on a theoretical model of flexible coping developed by the PI. We are also including the SexFlex Scale, which is a 6-item scale measuring sexual script flexibility when coping with sexual problems. To assess intervention acceptability, at post-treatment (T2), all participants will complete the CSQ-8 and additional questions assessing ease and helpfulness of participation and therapeutic rapport. Based on Borkovec's research, an intervention credibility measure ("Program Evaluation Form") will be completed after session 1 and again at the post-intervention assessment. All participants will complete surveys after session 1, 2, and 3, and again at the post-intervention survey assessing engagement with the material between sessions ("Materials Review Form"). Lastly, we have included a Coronavirus Impact Scale at baseline and six month follow-up to assess the effects the coronavirus pandemic has had on couples' lives, including their relationship and intimacy.

#### 4.4.3 Developmental Self-Report Survey Data (Exploratory Aim 2)

All data collected from participants in Exploratory Aim 2 (developmental survey study) will be collected using the Developmental Survey, which will be administered verbally using a standardized interview format. This verbal survey collects information on patients' reasons for lack of interest in participating, preferences for resources or programs addressing sexual/intimacy concerns, relationship length/quality, level of confidence in coping with sexual concerns, and race/ethnicity. In addition, if patients endorse the item from the screening script with regard to keeping their information from the screening, we will enter these information (e.g., age, breast cancer data) into our de-identified research files for further descriptive information about this sub-sample.

Table 2. Outcome Measures		Construct	# Items	Baseline	Session 1	Session 2	Session 3	Session 4	Post-Treatment	3-Month Follow-Up	6-Month Follow-Up
Measure											
Primary Outcome											
Female Sexual Function Index (FSFI)* 		Patient Sexual Function	19	X					X	X	X
Secondary Outcomes											
Female Sexual Function Index (FSFI)  International Index of Erectile Function (IIEF) 		Partner Sexual Function	19/15	X					X	X	X
Female Sexual Distress Scale-Revised (FSDS-R)*		Sexual distress	13	X					X	X	X
Miller Social Intimacy Scale (MSIS) 		Relationship Intimacy	17	X					X	X	X
Dyadic Adjustment Scale-7 item (DAS-7)		Relationship Quality	7	X					X	X	X
Patient Health Questionnaire-9 item (PHQ-9) 		Distress (depression)	9	X					X	X	X
Generalized Anxiety Disorder 7-item (GAD-7) 		Distress (anxiety)	7	X					X	X	X
Mediators											
Dyadic Sexual Communication Scale (DSCS) 		Sexual Communication	6	X					X		
Beliefs (self-efficacy) 		Self-Efficacy	7	X					X		
Additional Measures											
Demographic information for patient/partner		Demographic data	13/9	X							
Follow-up demographic/medical questions*		Changes to marital status/medical history	2							X	X
Self-Administered Comorbidity Questionnaire (SCQ) 		Medical comorbidity	14/15	X							

Sexual Self-View	Importance of Sexuality to Self	2 BL/ 1 FU	X					X	X	X
SexFlex Scale 	Sexual Script Flexibility	6	X					X		
PROMIS Intimate Activities/Use of Sexual Aids*	Intimate Activities & Use of Sexual Aids	8	X					X	X	X
Program Evaluation Form	Intervention Credibility	3		X				X		
Materials Review Form	Intervention Adherence	4		X	X	X		X		
CSQ-8 	Intervention Acceptability	8						X		
Additional Acceptability Questions 	Intervention Acceptability	14						X		
Skills Assessment**	Utilization of Skills	5						X	X	X
Coronavirus Impact Scale	Impact of Coronavirus Pandemic	19	X							X
Total # of items in baseline										
Patients	147									
Partners	119									
Total # of items in post-treatment survey										
Patients	134									
Partners	109									
Total # of items in 3-month survey										
Patients	88									
Partners	61									
Total # of items in 6-month survey										
Patients	107									
Partners	80									

\* indicates that only patients complete the measure; \*\*indicates that only IE participants complete the measure

#### 4.3 Overview of Randomization and Intervention Conditions

Couples will be randomized with an allocation ratio of 1:1 to either the IE or the Educational Control (Living Healthy Together) condition with stratification by age at diagnosis ( $\leq 45$  vs.  $> 45$ ) using the age obtained from the medical record (or by the patient during screening, if age at diagnosis is not available in the medical record). The statistician ([name]) will generate the randomization sequences using an automated randomization procedure in REDCap that limits prediction of allocation and protects masking of allocations. Randomization in blocks of four will guarantee that after every four assignments the study arms will have equal numbers. Separate randomization tables will be used for FCCC, Duke, and community participants to minimize the potential for unequal randomization by site.

Randomization will occur once both members of the couple have consented, completed baseline surveys, and are scheduled for their first intervention session. Randomization will occur centrally at the primary site by a staff member uninvolved in recruitment (to reduce the potential for bias in randomizing participants onto certain conditions). Once randomized, the couple will be sent sealed study materials along with the instructions to leave the envelopes sealed until they “meet” with their interventionist for session 1. It is important to keep the study condition a secret from participants until Session 1 to reduce the chances for unequal drop-out prior to Session 1, which could occur if patients/partners are more motivated to attend sessions in one study group as opposed to the other.

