If patients and/or partners are unable to complete the consent process online, they will be given the option to complete a written consent form either through US Mail or in person. If necessary, we will send self-addressed stamped return envelopes for the return of these consents along with paper and pencil surveys (if necessary), and will return signed copies to the couple.

In order to reduce the likelihood that web-based survey completion will lead to attrition, as can occur when the consent process takes place outside of an in-person clinic situation, the study team will engage in several reminder calls to the patient and/or partner to assist with completion (approximately 3 but no more than 6). These may include phone calls by the PI or recruiter, and email reminders, as well as attempting to set up an "appointment" with the patient and/or partner for consent and survey completion. Once the reminders have reached the maximum, we will cease to contact the patient or partner about the study and will note this in our files.

Once both members of the couple have completed consent, the couple is considered to be enrolled. If only one member of the couple completes consent and the other decides not to participate, this couple is not enrolled because only couples can participate in this intervention study. Individuals who consent to the study (through online web-based consent or paper consent through US Mail) will be sent a

photocopy of their consent form via US Mail and will be instructed to retain this consent form for their records.

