### **13.6 Statistical Analyses for Exploratory Aim 1 (Age and Race/Ethnicity as Intervention Moderators)**

In the primary analysis described above, we will explore (but do not expect to find) interactions between intervention effects and both age ( $\leq 45$  versus  $> 45$ ) and race/ethnicity (White versus non-White). Based

on pilot data, we estimate that approximately 30% and 25% of the sample will be classified as younger or non-White, respectively. Separate models will be fit for the 2 potential moderators. We will add age/race and interactions between the moderator, intervention, and time point in the regression model described in the Primary Aim. If the 3-way interaction between age/race, intervention, and follow-up time is significant, assessed via a likelihood ratio test, this will provide evidence that the treatment effect significantly differs by age or race. However, interaction effects not meeting statistical significance, but with an estimated magnitude  $> (.5 * \text{main effect})$  will suggest sub-threshold subgroup effects that we will consider in planning next steps including tailoring the IE intervention.

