
**Quality Assurance Procedures for Other Study Aspects.** First, to promote transparency, the trial will be registered on clinicaltrials.gov and a protocol paper will be published. Second, we have designed standardized procedures for every aspect of study administration, from the candidate screening process to administration of the study conditions. Third, all outcome measures have demonstrated excellent psychometric properties and have prior research supporting their appropriateness in the study population and sensitivity to interventions. Fourth, REDCap, a secure web-based application, will be

used for data collection and for randomization, with an automated procedure that limits prediction of allocation and protects masking of allocations. Finally, to facilitate unbiased data collection and analysis the following steps are taken: 1) the data analyst will conduct outcome data analyses on data in which study condition is masked; 2) outcome data collection is completed in an automated fashion using REDCap, minimizing the need for contact with participants to collect study data; 3) if needed, manual data collection will be completed by study staff for whom the participant's assignment is masked to the extent possible. On an annual basis, adverse events will be reviewed across study conditions. During the annual review of adverse events, the presence of significant between-group differences could potentially warrant unmasking of the study conditions by the study biostatistician. As with most behavioral interventions, study interventionists, intervention supervisors (site PI's), and participants are not blind to study condition.

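### A fixed, published block size of four lets someone with complete, current knowledge of one site-by-age list deduce up to about a third of its assignments

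*Combined protocol and SAP*

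**What the plan says.** Section 4.3 sets out the allocation: "Couples will be randomized with an allocation ratio of 1:1", to the IE or LHT "condition with stratification by age at diagnosis" (45 or younger versus older). It adds that "Separate randomization tables will be used for FCCC, Duke, and community participants", and that "Randomization in blocks of four will guarantee that after every four assignments the study arms will have equal numbers". The same paragraph describes the method as an "automated randomization procedure in REDCap that limits prediction of allocation and protects masking of allocations"; section 16.1 repeats that description. No varied or concealed block size is mentioned.

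The safeguards are also in section 4.3. Assignment is made centrally by someone who does not recruit. It follows consent and baseline surveys from both partners and the booking of session 1, and study materials stay sealed until that session. Section 16.1 adds that the PI and site PIs take no part in assessment, to protect blinding.

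Two passages bear on who could know and use earlier assignments. Section 16.1 states that "study interventionists, intervention supervisors (site PI's), and participants are not blind to study condition". Section 9.1, on reminders to couples who have yet to finish consent and the survey, says: "These may include phone calls by the PI or recruiter, and email reminders".

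**The concern.** Equality after every fourth assignment requires a constant block size, and the size is written in a protocol that the whole team reads. In a 1:1 block of four, the last assignment always follows from the first three, and the third follows from the first two when those are alike. Concealing the list and the current assignment does not prevent someone inferring the next assignment from those already known.

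The people placed to know past assignments overlap with those who may be in contact with couples not yet randomised. Section 16.1 has the PI taking part in regular supervision of the interventionists and lists supervisors as unmasked. Section 9.1 allows the PI to call couples about consent and surveys, both of which precede randomisation. Section 12.0 describes team meetings that cover recruitment progress as well as session delivery.

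At stake is selection by arm, even if unintended, through how persistently or when a couple is pursued. The primary outcome, the FSFI, is self-reported by participants who know their condition, so concealed allocation is one of the main protections left. Adjusting for baseline sexual function (section 13.2) would not correct for unmeasured differences such as a couple's motivation.

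**Working it through.** The documents give no figure for predictability, so there is none to reproduce.

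**Inputs from the plan.** Ratio 1:1, block size 4, three site tables and two age strata (section 4.3); 120 couples (section 13.8); about 30% in the younger stratum (section 13.6: "on pilot data, we estimate that approximately 30% and 25% of the sample will be classified as younger or non-White, respectively"). **Assumed:** the split of couples across FCCC, Duke and community, which the plan does not give by list. Splits of 50/35/15, equal thirds, 70/20/10 and 50/40/10 were tried.

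**1. Certain assignments in a complete block.** The six equally likely orders are AABB, ABAB, ABBA, BBAA, BABA and BAAB, giving 6 × 4 = 24 positions. The fourth is forced in all 6 orders. The third is forced in 2 (AABB, BBAA). The first and second never are. Share certain = (6 + 2)/24 = 8/24 = 33.3%.

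**2. Best-guess rate.** The chance of a correct guess at each position is:
- first: 1/2
- second: 2/3 (guess the opposite of the first)
- third: 1/3 × 1 + 2/3 × 1/2 = 2/3
- fourth: 1

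Mean = (1/2 + 2/3 + 2/3 + 1)/4 = 17/24 = 70.8%, against 50% by chance.

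**3. Knowledge that lags.** If the most recent assignment is unknown, only the fourth position can be certain, and only when the first two are alike: 1/3 × 1/4 = 1/12 = 8.3%. If the last two are unknown, nothing is certain (0%).

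**4. Six lists with incomplete last blocks.** There are 3 × 2 = 6 lists. Simulating 120 couples gives 31.2-31.4% certain across the assumed site splits, or about 120 × 0.312 = 37 couples, for an observer with complete, current knowledge of every list.

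**5. Ignoring the strata.** An observer who knows all earlier arms but pools the lists makes calls that look certain yet are right only about 55% of the time.

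**6. Varied block sizes.** Simulation against an observer who knows the set of sizes and all earlier assignments in the list, but not which size is in use (six-list columns use the 50/35/15 split):

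| Sizes | Certain, one list of 120 | Best guess, one list | Certain, six lists | Best guess, six lists |
|---|---|---|---|---|
| 4 only | 33.3% | 70.8% | 31.2% | 69.9% |
| 4, 6 | 5.5% | 69.2% | 5.8% | 68.2% |
| 2, 4, 6 | 4.1% | 70.2% | 3.7% | 69.3% |
| 4, 6, 8 | 2.2% | 68.0% | 2.2% | 66.9% |

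Varying the sizes removes most of the certainty but little of the guessing advantage.

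**7. Size of the smallest list.** With an assumed 15% community share, the younger community list has about 120 × 0.15 × 0.30 = 5.4 couples, so a block of 8 would often not complete there.

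**The case against.** The strongest reply is that fixed blocks of four are a common, defensible choice and that the plan surrounds them with real safeguards.

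- **Knowledge of the list is not documented.** Section 16.1 says only that supervisors are not blind. No section gives a PI an ordered list of assignments by site and age. Under section 4.3.1, supervision works from clinical notes without identifying information. Those notes come from sessions held after randomisation, so knowledge may lag, and step 3 shows how quickly certainty is then lost.
- **The means of using it are thin.** Reminder calls come after the recruiter has judged intent and understanding, and are capped at six. Breast cancer diagnosis, stage and treatment status are checked against medical records. Recruiters are not among those listed as unmasked. A PI could at most vary the persistence or timing of calls.
- **PIs are kept out of assessment.** Section 16.1 says so. Survey reminder calls by the PI under section 9.1 sit awkwardly with it. The two should be reconciled, but that is a separate matter.

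All of this stands, and it makes exploitation unlikely. It does not close the route, because the plan neither conceals the block size nor bars an unmasked supervisor from contacting couples before randomisation.

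A reader might infer that a third of assignments are certain to anyone who knows earlier ones. The documents do not support that: the knowledge must be complete, ordered, current and confined to the right one of six lists. A reader might also infer that the plan contradicts itself. It does not: it claims to limit prediction, not to eliminate it, and about two thirds of assignments stay uncertain even to a fully informed observer.

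**Conclusion.** The point holds as a conditional vulnerability. With one disclosed block size, up to one third of assignments can be deduced (about 31% with incomplete last blocks) by someone holding full, current knowledge of the relevant list. The figure is 8.3% if the latest assignment is unknown, and zero if the last two are. The one-third figure is exact and depends only on the ratio and block size. The 31% rests on assumed site splits but barely moves across them.

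The documents give no evidence that anyone holds such knowledge or that allocation has been influenced, so this is not a finding of bias. It is a cheap improvement that would bring the plan closer to its own aim of limiting prediction.

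**What to change.** For every block not yet started, have the statistician generate the REDCap tables with randomly varied small block sizes within each site-by-age list. Sizes 4 and 6 lower the best-guess rate more. Sizes 2, 4 and 6 leave slightly fewer certain assignments and suit the small lists better. Blocks of 8 suit the smallest lists poorly. Hold the sizes in a document that only the statistician can see.

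Replace the block-of-four sentence in section 4.3 with a statement that block sizes vary and are concealed from everyone involved in recruitment, supervision or delivery. Deleting the number four without changing the tables would achieve nothing, because the team has already read it. Blocks already under way stay as predictable as they are now until they close.

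The cost is one new set of tables and one protocol sentence. The largest possible imbalance within a list is half the largest block, so it rises from 2 to 3 couples when blocks of six are used. The effect on power is negligible. At the 92 analysable couples of section 13.8, an even split gives 1/46 + 1/46 = 0.0435. A 43/49 split gives 1/43 + 1/49 = 0.0437, about 0.4% more variance in the arm comparison.

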##### 4.3.1 Interventionists

All sessions will be conducted with the couple by trained interventionists with a Masters or doctoral degree in psychology or clinical social work and certified competent in the interventions by the PI. As established in our pilot trial, interventionist training consists of (a) background readings on key topics including breast cancer stages and treatments, common sexual and non-sexual side effects (e.g., stress, fatigue), sexual response, key techniques such as cognitive behavioral couple therapy and sensate focus therapy, theoretical models, and cultural issues in couple and sex therapy; (b) an in-person workshop or web conference which includes review of readings, protocols, and specific skills (e.g., communication skills training), role plays, and discussions, (c) listening to a tape of a well-executed case for each condition, and (d) complete IE and LHT test cases using intervention materials. During the trial, [name] and/or [name] will hold regular supervision sessions among the interventionists to ensure adequate quality of the delivered interventions. Interventionists will take standardized clinical notes on their sessions not containing identifying participant information and these notes will be discussed during supervision sessions. All supervision sessions are confidential; no identifiable information about participants is retained in clinical notes or supervision records. The quality assurance procedures regarding the delivery of the intervention are described further in section 16.0.

